3.3 Safety Objectives

The safety of participants will be measured throughout the study by assessing physiological and subjective drug effects, psychological distress, adverse events (AEs), and suicidality, repeatedly as described in the following steps. Summaries of safety data by study stage will be provided to the Medical Monitors for review during the study.

1. Explore correlations of subjective effects with the DEQ and cardiovascular effects with heart rate of each active dose of marijuana and placebo during introductory sessions.
2. Explore independent effects of each active dose of marijuana and placebo on blood pressure and body temperature during introductory sessions.
3. Assess independent effects of each active dose of marijuana and placebo on marijuana withdrawal symptoms during screening and Cessation 1 and 2.
4. Assess independent effects of each active dose of marijuana and placebo on problems associated with marijuana use during the study, including follow-up, with the CUDIT-R.
5. Evaluate the subjective effects of each active dose of marijuana and placebo in both controlled laboratory and outpatient settings, including ratings of unpleasant drug effects, using the DEQ and Daily Diary entries.
6. Assess independent effects of each active dose of marijuana and placebo on suicidality with the CSSRS on a weekly basis throughout the treatment period, and more frequently if needed.
7. Assess independent effects of each active dose of marijuana and placebo on whether and for how many days participants were incarcerated throughout the study.
8. Assess independent effects of each active dose of marijuana and placebo on whether and for how many days participants were hospitalized throughout the study.
9. Assess metabolites of alcohol use through urine testing at face-to-face visits.
10. Collect, review, and report Serious Adverse Events (SAEs) and AEs in accordance with FDA regulations and Section 8.0 of the protocol.

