5.1.2 Safety Measures

The Time-Line Follow-Back (TLFB) method will be used to track medical and non-medical drug/substance use [88, 89]. A retroactive TLFB assessment will be conducted to record substance use during the 90-days prior to the intake assessment during screening. It will then be repeated at the six-month follow-up visit to collect substance and medication use for each day since the last visit.

The Cannabis Use Disorders Identification Test-Revised (CUDIT-R) [90] is an eight-item self-report questionnaire used to assess problematic marijuana use within the past six-months. Questions assess consumption (frequency), marijuana abuse (e.g., use in hazardous situations, inability to fulfill obligations), marijuana dependence (e.g., not able to stop using, spending a lot of time obtaining, using, or recovering from use), and negative consequences of use (e.g., problems with memory or concentration). Responses are summed, thus providing a continuous score of problematic marijuana use. The CUDIT has demonstrated high internal consistency and acceptable test-retest reliability, high specificity and sensitivity, as well as satisfactory predictive power [90].

The Marijuana Withdrawal Checklist (MWC) [91, 92] will be used to assess the presence of marijuana withdrawal symptoms during prior periods of abstinence. The MWC will be labeled the Behavior Checklist to minimize expectancy effects. It lists 32 symptoms for which participants indicate severity on a four-point scale (0=not at all, 1=mild, 2=moderate, 3=severe). The symptom list comprises the valid items found in prior marijuana withdrawal studies and additional non-specific items to minimize response bias. During the intake assessment, participants will be instructed to indicate whether and to what degree they experienced each symptom during past periods of marijuana abstinence lasting at least 48 hours, if they are current marijuana users. Instructions will be slightly different during the study than during the intake assessment. Participants will be asked to rate how they have felt since last completing the questionnaires. Administered in this way, the MWC has been used effectively to detect reliable marijuana withdrawal effects in several prior studies [91-96]. A total withdrawal discomfort score (WDS) will be computed from the Checklist and will be the outcome variable for this measure. This summary score will include the symptoms reliably observed in prior marijuana withdrawal studies [97].

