| Visit Timing | Prescreen calls up to 2 months prior, in-person and Telemed procedures at least 2 weeks prior to Enrollment | 2 weeks after Screen 1 | 2 weeks after Screen 1, once cannabinoid results are obtained (Day 0 begins at Enrollment) | Occur on 2 consecutive days (Week 1 begins following Introductory Session 2) | Between start of Week 2 & start of Week 3 | Between end of Week 3 & start of Week 4 | Within 2 days of Primary Endpoint | Between end of Week 5 & start of Week 6 | Post cannabinoid results Occur on 2 consecutive days (Week 6 begins after Introductory Session 4) | Between start of Week 7 & start of Week 8 | Between end of Week 8 & start of Week 9 | Within 2 days of Secondary Endpoint | Between end of Week 10 & start of Week 11 | Post cannabinoid results Week 11-18 | 6 months after V12 (may take place over more than one day) |
| Blood Cannabinoid Biomarker | ✓ ^A | ✓ ^A | | | | | ✓ ^A | ✓ ^A | | | | ✓ ^A | ✓ ^A | | |
| Qualitative Urinary Drug | ✓ | ✓ | | ✓ | ✓ | | ✓ | ✓ | ✓ | ✓ | | ✓ | ✓ | ✓ | ✓ |
| Quantitative Urinary Drug | ✓ ^A | ✓ ^A | | | | | ✓ ^A | ✓ ^A | | | | ✓ ^A | ✓ ^A | | |
| Urinary EtG | ✓ | ✓ | ✓ | ✓ | ✓ | | ✓ | ✓ | ✓ | ✓ | | ✓ | ✓ | ✓ | |
| Urinary Pregnancy | ✓ | ✓ | | ✓ | ✓ | | ✓ | ✓ | ✓ | ✓ | | ✓ | ✓ | ✓ | |
| Clinical Labs | ✓ | | | | | | | | | | | | | | |
| ECG | ✓ | | | | | | | | | | | | | | |
| BP & BT | ✓ | | | ✓ ^C | Weekly | | ✓ | | ✓ ^C | Weekly | | ✓ | | Weekly | |
| Pulse Oximetry | ✓ | | | ✓ ^B | | | | | ✓ ^B | | | | ✓ | | |

[figure not shown]
A = Quantitative THC testing to be conducted in THC positive participants only. Blood and urine will be obtained and stored regardless of THC results. B = Completed before & immediately after self-administration and every 30 minutes thereafter until end of the visit. C= BP and BT will be obtained prior to self-administration, 30 minutes after starting self-administration and again at the end of each session, approximately four hours after starting self-administration.

Table 3: Time and Events (Study Measures)

| | | | | | Stage 1 | | | Cessation 1 | | Stage 2 | | | Cessation 2 | | Stage 3 | |
|---------------------|----------------------------|----------------------------|------------|-----------------------|---------------------|------------------|-------------|----------------------------|-----------------------|---------------------|--------------------|-------------|----------------------------|--------------------------------|---------------------------------|--|

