- e) The CI or qualified designee will assess prior substance use through the TLFB procedure for the past three months.
- f) The CI or qualified designee will assess GWB.
- g) The CI or qualified designee will administer the C-SSRS to assess suicide risk.
- h) The candidate will complete the PCL-5, MWC, CUDIT-R, BDI-II, and STOP-Bang.
- i) The IR will perform all relevant portions of the Structured Clinical Interview for DSM -5 Diagnoses – Research Version (SCID-RV) and SCID for personality disorders, which are module-based structured psychiatric interviews, to assess

- study eligibility. To establish reliability, the IR will have the option to video record the SCID interviews in as many instances as necessary.
- j) A physician, who may be the CI or qualified site staff, will perform a medical history directed physical examination. The examination will involve the following procedures:
- Blood pressure
 - Pulse
 - Height/weight
 - Body temperature
 - Examination of head, eyes, ears, nose, throat, skin, heart, lungs, abdomen and extremities
 - Brief neurological exam (cranial nerves 2-12, sensory, motor, reflexes and cerebellar function)
- k) The following clinical assessments will be collected and reviewed by the CI or qualified site staff:
- Electrocardiogram (ECG), the ECG will be used to establish eligibility and any clinically significant findings would be captured in the Medical History.
 - Serum electrolytes, metabolic profile, urinalysis and complete blood count. The clinical laboratory values will not be captured in the CRF, but will be used to establish eligibility and will be kept with the participant's source record. Clinically significant findings would be captured in the Medical History.
 - Qualitative Urine drug screening
 - Qualitative urine-dip EtG test to assess alcohol consumption
 - Urine-dip pregnancy test in participants with childbearing potential
 - Blood cannabinoid analysis will be collected (will be sent for analysis only if quantitative urine analysis is inconclusive in determining abstinence)
 - Quantitative Urine drug testing (will send for analysis only if pre- and post-cessation qualitative urine drug screens are positive for THC-COOH)
 - Pulse oximetry
- l) If, upon examination, there are questions raised about possible medical problems, the CIs will request a review of medical records and request additional tests or assessments as indicated.

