 - h) Peripheral blood will be collected for:
 - Blood Cannabinoid analyses
 - Biomarker analyses
 - i) The participant will bring their portable tablet to the study site. The site staff will review all video recording files, noting the time and date. Upon receipt, site staff will verify participant identity, safety, and compliance through review of video recordings, as well as telephone contact reports. Upon review, if any days are missing from recordings, participants will be re-trained by site staff. The portable device will be cleared of content and returned to the participant.
 - j) The participant will bring their Actigraph to the study site. The site staff will copy all recording files, note the time and date stamp and save for analysis. The Actigraph memory will be cleared, the device charged and returned to the participant to use for the next week. Upon analysis, if any days are missing from recordings, participants will be re-trained the next time they are contacted by site staff.
 - k) The site staff will instruct the participant to complete the Daily Diary to assess, sleep patterns, continuing substance and medication use patterns and AEs during cessation.
 - l) The site staff and participant will discuss the two-week period of cessation of marijuana use.
 - m) One week after the beginning of cessation, participants will complete the MWC , IDAS, ISI, IPF, WBR, and PCL-5 electronically. Participants will be reminded to complete self-report measures in a timely manner.
 - n) One week after the beginning of cessation the CI or site staff will telephone the community observer to complete the WBR assessment.

5.2.11 Re-Baseline Evaluation at end of Cessation 1 (Visit 7) and Cessation 2 (Visit 14)

At the end of the Cessation period, two weeks after completion of the primary/secondary endpoint assessment, participants will visit the study site.

- a) The participant will complete the IDAS, ISI, IPF (past 2 weeks), WBR, PCL-5 and the MWC.
- b) The participant will complete the CUDIT-R only at Visit 14.
- c) Site staff will contact the community observer for completion of the WBR.
- d) The CI or qualified site staff will administer the C-SSRS and GWB.
- e) Participants will meet with the IR for a 60 to 90 minute evaluation, either in a face-to-face or telemedicine meeting to administer the last week CAPS-5.

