5.2.13 Long-term Follow-up

This visit will be conducted 6 months after end of Cessation 2. Visit may take place over more than one day, and will be conducted via telemedicine or in person at the study site.

- a) One week before the visit, site staff will clear the Actigraph memory, charge the device and mail it to the participant to use for the week prior to the six-month follow-up.
- b) On the day of the visit, inquire about any changes in the participant's health to obtain resolution on any outstanding AEs.
- c) Collect information on any changes in psychotherapy, healthcare utilization, and medications for the participant.
- d) Substance use will be ascertained using the TLFB procedure for the past six

- months.
- e) Participants will meet with the independent rater for a 60 to 90 minute evaluation. either in a face-to-face or telemedicine meeting to administer the last month CAPS-5.
 - f) The participant will complete the IDAS, ISI, IPF (last month), WBR, PCL-5, MWC and CUDIT-R.
 - g) Site staff will contact the community observer for completion of the WBR.
 - h) The CI or qualified site staff will administer the C-SSRS and GWB.
 - i) The participant will mail or bring their Actigraph to the study site. The site staff will copy all recording files, note the time and date stamp and save for analysis. Participants will not be given the Actigraph after this visit.
 - j) A urinary drug test will be administered to test for drugs of abuse.
 - k) The participant will complete the LTFU questionnaire.
 - l) Upon completion of this visit, and after site staff obtain all outstanding data, participants will complete the study.

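### Safety Objective 4 promises separate placebo and dose effects on CUDIT-R, but the first repeat comes after everyone continuing has had active marijuana, so a plain Stage 1-arm comparison would be contaminated

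*Protocol*

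**What the plan says.** Section 3.3, item 4, commits the study to estimating the effect of "each active dose of marijuana and placebo on problems associated with marijuana use during the study, including follow-up, with the CUDIT-R".

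Section 5.1.2 describes the CUDIT-R as an eight-item questionnaire "used to assess problematic marijuana use within the past six-months".

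It is scheduled three times, and the CUDIT-R row of Table 3 agrees with the visit text:
- **Screen 1 (Section 5.2.2):** "The candidate will complete the PCL-5, MWC, CUDIT-R, BDI-II, and STOP-Bang".
- **Re-baseline visits (Section 5.2.11):** "The participant will complete the CUDIT-R only at Visit 14". It is therefore not given at Visit 7, the end of Cessation 1. Table 1 places Visit 14 "Between end of Week 10 & start of Week 11".
- **Long-term follow-up (Section 5.2.13):** "The participant will complete the IDAS, ISI, IPF (last month), WBR, PCL-5, MWC and CUDIT-R". That section says "This visit will be conducted 6 months after end of Cessation 2", whereas Tables 1 and 2 count six months from Visit 12.

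Sections 4.0 and 4.2 remove placebo from Stage 2. Every participant is re-randomised to an active product different from the Stage 1 product. Section 12.0 includes CUDIT-R in a list of weekly assessments for exploratory repeated-measures modelling and leaves the method to the statistical analysis plan.

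**The concern.** A separate effect for placebo and for each concentration needs a score that can be attributed to one assigned product. The schedule provides none. The only score taken around the treatment period follows both stages, and its recall period also reaches back well before the study.

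The obvious analysis would group Visit 14 scores by Stage 1 arm and read the placebo arm as a control. By then that arm has had three weeks of access to active marijuana. The other arms have had a different mix of Stage 2 products, because each excludes its own Stage 1 product. Section 7.3 lists abuse liability among the chief risks, so a shrunken active-versus-placebo difference on this scale could be read as reassurance that the data do not give.

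**Working it through.** **1. What each recall window covers.** Inputs: three-week stages, each followed by two weeks of cessation (Section 2.1), and recall of six months, about 26 weeks (Section 5.1.2). Count weeks from the start of Week 1: Stage 1 = 0 to 3, Cessation 1 = 3 to 5, Stage 2 = 5 to 8, Cessation 2 = 8 to 10. The window is (t − 26, t).

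| Score at | Window | Before Week 1 | Stage 1 | Cess. 1 | Stage 2 | Cess. 2 | Later |
|---|---|---|---|---|---|---|---|
| Visit 14, t = 10 | −16 to 10 | 16 | 3 | 2 | 3 | 2 | 0 |
| Follow-up, 6 months after Visit 12, t = 34 | 8 to 34 | 0 | 0 | 0 | 0 | 2 | 24 |
| Follow-up, 6 months after Cessation 2, t = 36 | 10 to 36 | 0 | 0 | 0 | 0 | 0 | 26 |
| Visit 7 (not scheduled), t = 5 | −21 to 5 | 21 | 3 | 2 | 0 | 0 | 0 |

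At Visit 14, 16/26 = 62% of the window precedes Week 1 and 3/26 = 12% is Stage 1. Either follow-up window includes the optional Stage 3 and later use. Week 1 starts shortly after enrolment, a small offset that is ignored here.

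**2. What a plain Stage 1-arm comparison estimates at Visit 14.** Let h, b and m be the effects of High THC, High CBD and THC/CBD on the score. For illustration, take them as additive and equal in either stage. Under Table 4 as it reads, the placebo arm is split between High THC and High CBD:
- High THC − placebo = h + (b + m)/2 − (h + b)/2 = (h + m)/2
- High CBD − placebo = b + (h + m)/2 − (h + b)/2 = (b + m)/2
- THC/CBD − placebo = m + (h + b)/2 − (h + b)/2 = m

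Table 6 expects 25, 25 and 26 participants per Stage 2 product. With 19 per Stage 1 arm, a two-way placebo split gives 28.5, 28.5 and 19. A three-way split gives 9.5 + 9.5 + 19/3 = 25.3 each, which fits Table 6. Under the three-way split:
- High THC − placebo = h + (b + m)/2 − (h + b + m)/3 = 2h/3 + (b + m)/6, and likewise for the other products.

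If only High THC acts (b = m = 0), the contrast shows h/2 under Table 4 or 2h/3 under Table 6. Under the three-way split, the product with the largest effect is understated unless all three effects are equal. Under the two-way split, High THC or High CBD is understated when its effect exceeds m, and THC/CBD is undistorted. If the score registers any active exposure rather than accumulating, and the products act alike, all arms look the same and the contrast is zero.

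The error can also run the other way. With b = 0 and h = m, High CBD would show m/2 under Table 4 although it does nothing.

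**3. What remains estimable.** Stage 2 is re-randomised within Stage 1 arms, so Stage 2 product can be held fixed. Under Table 4:
- High THC versus placebo, among those given High CBD in Stage 2.
- High CBD versus placebo, among those given High THC in Stage 2.
- THC/CBD versus placebo, among those given either of these.

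An additive Stage 1 + Stage 2 model has 4 + 3 − 1 = 6 parameters for 8 connected cells, so all Stage 1 contrasts are identified. Cells hold about 19/2 = 9.5 participants, or 19/3 = 6.3 in the placebo arm under a three-way split, before Stage 2 dropout.

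**The case against.** A reader might infer that the placebo contrast on CUDIT-R cannot be estimated at all. The documents do not support that. Re-randomisation within Stage 1 arms leaves groups that share a Stage 2 product and differ only in Stage 1 product. This point stands in full. The remaining limits are small cells, restriction to participants who complete Stage 2, and, for the pooled model, an additivity assumption that the protocol does not state.

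A reader might also treat the 62% pre-study share of the window as a bias. It is not. Stage 1 is randomised, so earlier use is balanced in expectation. A screening score exists for adjustment, and entry requires a CUDIT-R below 8 and two weeks of verified abstinence. The long window dilutes the contrast without tilting it, and calendar weeks are not known to act as weights on the score.

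The objective refers to problems during the study including follow-up, which suits a cumulative measure. That is fair for an overall description, but not for separate effects of each dose and placebo.

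Nothing says that an unadjusted Stage 1-arm comparison will be reported. Section 12.0 calls these analyses exploratory and defers the method to a plan not seen here. That plan could condition on Stage 2 product, but it could not create a score that was never collected.

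Other measures, such as the DEQ, the withdrawal checklist at Visits 6 and 7, and adverse events by concentration, do give Stage 1 data against placebo. This limits the harm. Finally, Section 5.3 allows outcome evaluations after withdrawal where possible, so a few placebo participants might give unscheduled placebo-only scores. They would be few and selected.

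**Conclusion.** The point holds in a limited form. Safety Objective 4 is not delivered as worded: no scheduled post-baseline CUDIT-R score reflects placebo or one concentration alone. A plain Stage 1-arm comparison at Visit 14 is contaminated by Stage 2 exposure that differs by arm. It tends to understate the active-versus-placebo difference for the most harmful product, to one half or two thirds of its size if High THC alone acts. Those fractions assume additive effects that are equal in both stages. The direction is a tendency and depends on how the products compare.

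The follow-up score covers no Stage 1 or Stage 2 use under either dating of the visit, so it cannot supply the missing contrast directly.

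The contrast is weak and conditional, but not impossible. The matter deserves correction. It is modest in weight, because CUDIT-R is one of several safety measures in a pilot study.

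**What to change.** 1. Restate Safety Objective 4 as change in CUDIT-R from screening, described by Stage 1-Stage 2 sequence.
2. Allow a Stage 1 product-versus-placebo comparison only when it is conditioned on Stage 2 product (same-product groups or the additive model) and adjusted for screening CUDIT-R. Label it exploratory.
3. State that an unadjusted Stage 1-arm comparison at Visit 14 or long-term follow-up will not be presented as a placebo contrast.
4. In Section 12.0, take CUDIT-R out of the list of weekly assessments.

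These are wording changes with almost no cost and no new data.

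**Optional, if a direct placebo contrast is wanted:** add the eight items at the existing Visit 7, with recall limited to Stage 1 and Cessation 1. Adding the standard form there would avoid Stage 2 contamination, but 21 of its 26 recall weeks would still precede Week 1. Table 3 already uses shortened recall for the IPF, the withdrawal checklist and the CAPS-5. The cost is a short extra form and a departure from the standard instrument, so the validation cited in Section 5.1.2 would not carry over automatically. That is a trade-off for the sponsor to weigh.

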5.1.3 Process Measures

The Daily Diary is an instrument developed by the sponsor to track AEs and assess daily use of study marijuana as well as other substances. The Daily Diary will be an electronic data capture form completed on an electronic device. Information collected with this diary will include participants' self reported quality and duration of sleep, the daily amount of marijuana used concomitant use of alcohol, medications, or other drugs, as well as AEs. Daily diary reports will be confirmed and verified by phone contact, reviewing video of participants' self-administration of marijuana, and qualitative urine drug testing at the sites.

The LTFU questionnaire is a sponsor-developed self-report instrument that will gather information on current psychiatric health and wellbeing, including the occurrence of new traumatic events, and questions concerning the number and type of new treatments for PTSD the participant has undergone since his or her final visit during the treatment period. The LTFU questionnaire takes approximately five minutes to complete, and will be completed by the participants at the six-month follow-up.

Laboratory testing of blood/urine cannabinoids will be conducted by an accredited laboratory with an appropriately sensitive, specific and validated assay, as specified in Section 10.2. Peripheral blood samples will be collected and stored for biomarker analysis of cannabinoids (THC, 11-OH-THC, THC-COOH), CBD metabolites and inflammation markers with appropriately sensitive, specific and validated assays for CRP, IL-1 β , and IL-6. Peripheral blood will be drawn at specified times in the Time and Events Labs table and analyzed according to procedures described in Section 10.0.

Questions regarding the belief of condition assignment and certainty of the belief will be asked of site staff and participants at the End of Stage 1 and End of Stage 2. These beliefs are collected as a part of the sponsor's ongoing initiative to optimize the double-blind as a part of drug development studies.

Table 1: Time and Events (Administrative Procedures)

| | Screen | Baseline | | Stage 1 | | | Cessation 1 | | Stage 2 | | | Cessation 2 | | Stage 3 | LTFU |
|---------------------------------|---|----------------------------|--|---|---|--|-----------------------------------|---|--|---|---|-------------------------------------|---|-------------------------------------|--|
| | | | | Introductory Sessions | Self-administration | Primary Endpoint | Cessation 1 | Stage 2 Baseline | Introductory Sessions | Self-administration | Secondary Endpoint | Cessation 2 | LTFU Baseline | Stage 3 (optional) | |
| Visit # | Prescreen & Screen 1 | Screen 2 | Enrollment | V1 & V2 | V3 & V4 | V5 | V6 | V7 | V8 & V9 | V10 & V11 | V12 | V13 | V14 | V15-V23 (as needed) | LTFU |
| Type of Visit | Telemed Visit & Site Visit | Telemed Visit & Site Visit | Site Visit | Site Visit | Weekly Site Visits | Telemed Visit | Site Visit | Telemed Visit & Site Visit | Site Visit | Weekly Site Visits | Telemed Visit | Site Visit | Telemed Visit & Site Visit | Weekly Site Visits (as needed) | Telemed Visit and/or Site Visit |
| Visit Timing | Prescreen calls up to 2 months prior, in-person and Telemed procedures at least 2 weeks prior to Enrollment | 2 weeks after Screen 1 | 2 weeks after Screen 1, once cannabinoid results are obtained (Day 0 begins at Enrollment) | Occur on 2 consecutive days (Week 1 begins following Intro Session 2) | Between start of Week 2 & start of Week 3 | Between end of Week 3 & start of Week 4 May be combined with V6 | Within 2 days of Primary Endpoint | Between end of Week 5 & start of Week 6 | Post cannabinoid results Occur on 2 consecutive days (Week 6 begins after Intro Session 4) | Between start of Week 7 & start of Week 8 | Between end of Week 8 & start of Week 9 May be combined with V13 | Within 2 days of Secondary Endpoint | Between end of Week 10 & start of Week 11 | Post cannabinoid results Week 11-18 | 6 months after V12 (may take place over more than one day) |
| Phone Screen | ✓ ^A | | | | | | | | | | | | | | |
| ICF | ✓ | | | | | | | | | | | | | | |
| Brief Medical & Psych History | ✓ | | | | | | | | | | | | | | |
| Directed Physical | ✓ | | | | | | | | | | | | | | |
| Collect Therapy & Medications | ✓ | | ✓ | ✓ | ✓ | | ✓ | ✓ | ✓ | ✓ | | ✓ | ✓ | ✓ | ✓ |
| Enrollment & Randomization | | | ✓ | | | | | | | | | | | | |
| Training on Self-Administration | | | | ✓ | | | | | ✓ | | | | | | |
| Video Data Review | | | | | Weekly | | | | | Weekly | | | | Weekly | |
| Dispense Drug | | | | Post V2 | Weekly | | | | Post V9 | Weekly | | | | Weekly | |
| Weigh Unused Marijuana | | | | | Weekly | | ✓ | | | Weekly | | ✓ | | Weekly | |
| Phone Calls | | | | | Weekly ^B | | Weekly ^C | | | Weekly ^B | | Weekly ^C | | Weekly ^D | |
| Collect AEs | | | ✓ | ✓ | ✓ | | ✓ | ✓ | ✓ | ✓ | | ✓ | ✓ | ✓ | ✓ |

A= Initial phone screen with coordinator, secondary phone screen to be performed by CI/Qualified designee or Clinician. B= Participants will have 3 days of phone contact after each second introductory session in Stage 1 and Stage 2. (more contact may occur as needed) Participants will have a mid-week phone contact during Stage 1 and Stage 2 self-administration weeks 2 and 3. C= Participants will be contacted one week after the beginning of Cessation. D= Participants will have a mid-week phone contact.

Table 2: Time and Events (Laboratory Procedures)

| | Screen | Baseline | | Stage 1 | | | Cessation 1 | | Stage 2 | | | Cessation 2 | | Stage 3 | |
|------------------------------------|---|----------------------------|--|--|---|---|-----------------------------------|---|---|---|---|-------------------------------------|---|-------------------------------------|--|
| | | Prescreen & Screen 1 | Screen 2 | Enrollment | Introductory Sessions V1 & V2 | Self-administration V3 & V4 | Primary Endpoint V5 | Cessation 1 V6 | Stage 2 Baseline V7 | Introductory Sessions V8 & V9 | Self-administration V10 & V11 | Secondary Endpoint V12 | Cessation 2 V13 | LTFU Baseline V14 | Stage 3 (optional) V15-V23 (as needed) |
| Visit # | Prescreen & Screen 1 | Screen 2 | Enrollment | V1 & V2 | V3 & V4 | V5 | V6 | V7 | V8 & V9 | V10 & V11 | V12 | V13 | V14 | V15-V23 (as needed) | LTFU |
| Type of Visit | Telemed Visit & Site Visit | Telemed Visit & Site Visit | Site Visit | Site Visit | Weekly Site Visits | Telemed Visit | Site Visit | Telemed Visit & Site Visit | Site Visit | Weekly Site Visits | Telemed Visit | Site Visit | Telemed Visit & Site Visit | Weekly Site Visits (as needed) | Telemed Visit and/or Site Visit |
| Visit Timing | Prescreen calls up to 2 months prior, in-person and Telemed procedures at least 2 weeks prior to Enrollment | 2 weeks after Screen 1 | 2 weeks after Screen 1, once cannabinoid results are obtained (Day 0 begins at Enrollment) | Occur on 2 consecutive days (Week 1 begins following Introductory Session 2) | Between start of Week 2 & start of Week 3 | Between end of Week 3 & start of Week 4 | Within 2 days of Primary Endpoint | Between end of Week 5 & start of Week 6 | Post cannabinoid results Occur on 2 consecutive days (Week 6 begins after Introductory Session 4) | Between start of Week 7 & start of Week 8 | Between end of Week 8 & start of Week 9 | Within 2 days of Secondary Endpoint | Between end of Week 10 & start of Week 11 | Post cannabinoid results Week 11-18 | 6 months after V12 (may take place over more than one day) |
| Blood Cannabinoid Biomarker | ✓ ^A | ✓ ^A | | | | | ✓ ^A | ✓ ^A | | | | ✓ ^A | ✓ ^A | | |
| Qualitative Urinary Drug | ✓ | ✓ | | ✓ | ✓ | | ✓ | ✓ | ✓ | ✓ | | ✓ | ✓ | ✓ | ✓ |
| Quantitative Urinary Drug | ✓ ^A | ✓ ^A | | | | | ✓ ^A | ✓ ^A | | | | ✓ ^A | ✓ ^A | | |
| Urinary EtG | ✓ | ✓ | ✓ | ✓ | ✓ | | ✓ | ✓ | ✓ | ✓ | | ✓ | ✓ | ✓ | |
| Urinary Pregnancy | ✓ | ✓ | | ✓ | ✓ | | ✓ | ✓ | ✓ | ✓ | | ✓ | ✓ | ✓ | |
| Clinical Labs | ✓ | | | | | | | | | | | | | | |
| ECG | ✓ | | | | | | | | | | | | | | |
| BP & BT | ✓ | | | ✓ ^C | Weekly | | ✓ | | ✓ ^C | Weekly | | ✓ | | Weekly | |
| Pulse Oximetry | ✓ | | | ✓ ^B | | | | | ✓ ^B | | | | ✓ | | |

[figure not shown]
A = Quantitative THC testing to be conducted in THC positive participants only. Blood and urine will be obtained and stored regardless of THC results. B = Completed before & immediately after self-administration and every 30 minutes thereafter until end of the visit. C= BP and BT will be obtained prior to self-administration, 30 minutes after starting self-administration and again at the end of each session, approximately four hours after starting self-administration.

Table 3: Time and Events (Study Measures)

| | | | | | Stage 1 | | | Cessation 1 | | Stage 2 | | | Cessation 2 | | Stage 3 | |
|---------------------|----------------------------|----------------------------|------------|-----------------------|---------------------|------------------|-------------|----------------------------|-----------------------|---------------------|--------------------|-------------|----------------------------|--------------------------------|---------------------------------|--|
| | Screen | Baseline | | Introductory Sessions | Self-administration | Primary Endpoint | Cessation 1 | Stage 2 Baseline | Introductory Sessions | Self-administration | Secondary Endpoint | Cessation 2 | LTFU Baseline | Stage 3 (optional) | LTFU | |
| Visit # | Prescreen & Screen 1 | Screen 2 | Enrollment | V1 & V2 | V3 & V4 | V5 | V6 | V7 | V8 & V9 | V10 & V11 | V12 | V13 | V14 | V15-V23 (as needed) | LTFU | |
| Type of Visit | Telemed Visit & Site Visit | Telemed Visit & Site Visit | Site Visit | Site Visit | Weekly Site Visits | Telemed Visit | Site Visit | Telemed Visit & Site Visit | Site Visit | Weekly Site Visits | Telemed Visit | Site Visit | Telemed Visit & Site Visit | Weekly Site Visits (as needed) | Telemed Visit and/or Site Visit | |
| SCID | ✓ | | | | | | | | | | | | | | | |
| CAPS-5 | | ✓ | | | | ✓ | | ✓ ^F | | | ✓ | | ✓ ^F | | ✓ | |
| BDI-II | ✓ | | | | | | | | | | | | | | | |
| IDAS | | | ✓ | | ✓ | | ✓ | ✓ | | ✓ | | ✓ | ✓ | | ✓ | |
| ISI | | | ✓ | | ✓ | | ✓ | ✓ | | ✓ | | ✓ | ✓ | | ✓ | |
| IPF ^G | | | ✓ | | | | ✓ | ✓ | | | | ✓ | ✓ | | ✓ | |
| PCL-5 ^E | ✓ | | ✓ | | ✓ | | ✓ | ✓ | | ✓ | | ✓ | ✓ | | ✓ | |
| ACT | | ✓ ^C | | ✓ | ✓ | | ✓ | ✓ | ✓ | ✓ | | ✓ | ✓ | | ✓ ^D | |
| MWC ^H | ✓ | | ✓ | | | | ✓ | ✓ | | | | ✓ | ✓ | | ✓ | |
| CUDIT-R | ✓ | | | | | | | | | | | | ✓ | | ✓ | |
| DEQ | | | | ✓ ^A | ✓ ^B | | | | ✓ ^A | ✓ ^B | | | | ✓ ^B | | |
| Daily Diary | | | ✓ | ✓ ^B | ✓ ^B | ✓ | ✓ | ✓ | ✓ ^B | ✓ ^B | ✓ | ✓ | ✓ | ✓ ^B | | |
| CSSRS & GWB | ✓ | | ✓ | ✓ | ✓ | | ✓ | ✓ | ✓ | ✓ | | ✓ | ✓ | ✓ | ✓ | |
| WBR | | ✓ | | | ✓ | | ✓ | ✓ | | ✓ | | ✓ | ✓ | ✓ | ✓ | |
| STOP-Bang | ✓ | | | | | | | | | | | | | | | |
| Belief of Condition | | | | | | | ✓ | | | | | ✓ | | | | |
| LTFU Questionnaire | | | | | | | | | | | | | | | ✓ | |
| TLFB | ✓ | | | | | | | | | | | | | | ✓ | |

A = Completed before & immediately after self-administration and every 30 minutes thereafter until end of session. B = Completed immediately after each self-administration C = Actigraphy use must begin one week prior to the first Introductory Session. D = Final week only. E= Will measure past week. LEC plus Criterion A to be assessed at baseline only. F= CAPS-5 assessments at these timepoints will measure the last week.G= Visit 6 will be based on past 3 weeks, Visit 7 will be based on the past 2 weeks, Visit 13 will be based on the past 3 weeks, Visit 14 will be based on the past 2 weeks, LTFU will be based on the last month. H= Will measure the past 2 weeks.

Figure 1: Summary of Events

